Pregnant women will be recruited via three possible means: 1) Recruitment posters and pamphlets (Appendix B, Recruitment poster and pamphlet) distributed in clinics associated with the CHU Ste Justine; 2) Obstetrician, psychiatrists or general practitioner in clinics associated with the CHU Ste Justine; or 3) Advertisements posted on various social media (Facebook, Instagram; Twitter, etc.). Interested women will either 1) connect to a web page and fill a contact form (Appendix C); or 2) contact us by phone, text message or email.

The research coordinator will contact women referred by practitioners or through advertisement. The study will be explained and a consent form (Appendix F, Consent forms) will then be sent through REDCap. Participants will sign virtually. Then, they will respond by telephone to the eligibility questionnaire (5 min.), including the EPDS (50) psychosis screening questionnaire and self reported substance abuse problem. Those with subclinical levels of depression (EPDS 9-12) and without psychosis and substance abuse problem will be randomized via REDCap and informed of their group allocation.

Partners Recruitment

During the recruitment phone call with pregnant women, the research coordinator will explain the possibility of partners to participate in the study and the advantage of it. A partner can be the spouse or any other significant person who will accompany the pregnant woman during pregnancy and after childbirth. It is recommended to keep the same person for the duration of the course. The research coordinator will ask the pregnant women to identify her partner and if he or she is at home at this moment, he or she will be invited to join the call. Partners will be eligible only if the pregnant woman signed the consent form and is eligible for the study. If the partner is absent, the research coordinator will ask for his or her email or telephone number. If the pregnant woman sign the consent form and is eligible for the study, an invitation will be sent to briefly explain the project and to ask them if they accept us to call them to give more information and recruit them if interested. The research coordinator will then contact those interested, explain the study and send an email with the consent form.

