Recruited pregnant women and partners will receive a notification with a link to answer the baseline questionnaire (Appendix E, Baseline and follow-up questionnaires) online and our contact information to take an appointment with a research assistant if they prefer to answer the questionnaire on the phone. After completion of the baseline questionnaire, access to the intervention website will be authorized.

[figure not shown]
Planned recruitment rate

The participant recruitment rate depends on two factors: 1) capacity to recruit pregnant women with subclinical depressive symptoms (EPDS 9-12); 2) participant acceptance of the trial. In one of our ongoing mental health studies in pregnant women, 374 (22.1%) participants with EPDS scores 9-12 (out of 1695 assessed) were recruited over social media in a two-week period (i.e., 185/week). Within Sainte Justine's obstetrics clinics, 25 – 30 women/week are assessed with the EPDS. Therefore, we expect to recruit around five women/week at the beginning of our trial. When we will expand our recruitment on social media, we estimate to recruit $n = 15$ women per week willing to accept randomization. The recruitment period should last a total of approximately ten months. Thus, an average of 25 women per month would enter the intervention under the guidance of one of 3 *coaches* (i.e., 8 women/*coach*). Intervention activities will take 18-20 months. Figure 2 presents the schedule of recruitment and intervention implementation.

Participating centers.

The trial is based at Sainte Justine Hospital (CHU Ste-Justine), the largest mother-child hospital in Quebec. Affiliated obstetric clinics will refer patients to the study site (Appendix G, Letters of Support). These clinics provide an ideal setting for recruiting mothers of diverse ethnic backgrounds.

Figure 2. Schedule of recruitment and intervention implementation

¹ First women to complete will begin the trial at 25 gestational weeks in the first wave of recruitment

² Last women to complete will begin the trial at 12 gestational weeks in the last wave of recruitment

Sample

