Duration of treatment period. The typical duration of the program is 2 months (8 weeks) during pregnancy and 2 months over the first 3 months of the baby's life. The two postpartum sessions aim to lend support during the challenges of the postpartum period. The proposed frequency of nurse telephone follow-up is once/week in pregnancy and once/month in postpartum, but this can be adapted to the needs of the woman and/or her partner. Figure 3 presents the intervention and assessments.

Figure 3. Frequency and duration of the follow-up

Participants will fill out questionnaires (online or by telephone) at T₀ (12-25 weeks' gestation), T₁ (3 months' postpartum), and T₂ (6-months postpartum) to assess baseline values and trial outcomes, respectively. If we show efficacy at 3 months' postpartum (primary outcome), we will seek funding to follow families over the early childhood years. Real date of birth will be assessed six weeks after the estimated date of birth.

Coaches training and supervision. PhD students in clinical psychology and Master's students in nursing are ideally suited to conduct the 10 follow-up calls. They will be supervised by our multidisciplinary team (2 nurses, 2 clinical psychologists, and 2 psychiatrists). All coaches will receive 5-day training in perinatal mental health and use of the intervention material. Procedures for calls will be outlined in the intervention manual. The supervision team will oversee implementation as part of the Executive Committee. Intervention sessions will be audiotaped and randomly reviewed by the supervision team to ensure compliance with the material.

Virtual intervention without telephone support (control group). The control group will receive a fully automated version of the virtual intervention

Data Collection

We will conduct a comprehensive assessment of perinatal maternal mental health and functioning as well as factors that may modify the impact of the intervention. The chosen assessment tools are validated (French and English), require low levels of literacy and take only 15-30 minutes to complete (Appendix L, Description of assessment tools). They have been used previously with pregnant women and examined for clarity, comprehension, and ease of use. The questionnaires will be completed online via REDCap or over the telephone with a research assistant blinded to group allocation depending on maternal preference, and with the partner if the woman so chooses.

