Secondary outcomes. Participant and partner assessments at baseline, T₁ and T₂. The proposed intervention is based on CBT principles used to treat both anxiety and depression. As anxiety is highly correlated with perinatal depression, it is an important secondary outcome. **Generalized anxiety.** The proposed intervention is based on CBT principles used to treat both anxiety and depression. As anxiety is highly correlated with perinatal depression, it is an important secondary outcome. Anxiety will be assessed at all 3 time points, using the Generalized Anxiety Disorder 7-item (GAD-7) scale, an extensively validated self-report instrument (75-77). **Anxiety related to pregnancy** will be measured with the 10-item Pregnancy-specific anxiety scale (PRAQ-R2) (78, 79) at baseline. **Stress** will be assessed using the 10-item form of the Perceived Stress Scale, at six months postpartum (80, 81). **Well Being** will be evaluated with the 5-item WHO-5 well-being index at T₁ (82). **Self-efficacy** will be assessed using the 10-item General Self-Efficacy Scale (GSE) at 3 months postpartum (83, 84). **Self-Compassion** will be measured with the 12-item shortened version of the Self-Compassion Scale (SCS) (85-87), at 3 months postpartum. **Sleep.** Sleep may improve as a result of the increased capacity for relaxation, mindfulness, and emotional regulation fostered by the intervention. At 3 months postpartum, we will assess sleep quality, a critical aspect of perinatal maternal health, using the 19-item Pittsburgh Sleep Quality Index (PSQI) (88, 89), a self-report over a one-month interval with very good psychometric properties and validated for use during postpartum (90). **Tobacco, alcohol and drug use** will be self-reported at baseline and 3 months postpartum. **Social Adjustment** will be assessed using the 14-item screener version of the Social Adjustment Scale – Self-report (SAS-SR) (91, 92). Six major areas are covered: work (paid or unpaid), social and leisure activities, relationships with extended family, role as marital partner, role as a parent, and role within the family unit (including perceptions about economic functioning). For this study, we will only use the work subscale at 3 months postpartum. **Marital satisfaction** will be evaluated with the short version of the Dyadic Adjustment Scale (DAS-7) (93-95) at 3 months postpartum. **Co-parenting.** The proposed intervention is partner-inclusive and, as such, may improve co-parenting quality (the extent to which parents work together and agree on childcare and education). We will use a brief 14-item version of the Coparenting Relationship Scale (75) (e.g., partner pays a great deal of attention to our child; partner appreciates how hard I work at being a good parent) at 3 months postpartum. **Social Support** will be assessed at 6 months postpartum using the 10-item Social Provisions Scale (SPS-10) on emotional

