The trial manager will obtain signed confidentiality agreements from research assistants. All baseline and outcome data will be collected via online questionnaires using REDCap and stored in an anonymized database on a secure server at URCA. Data will remain strictly confidential and will not be disclosed to members of our intervention team or the partner. Data safety will be maximized through electronically protecting access to computers and servers, use of fire walls. Coding standards will be developed by the executive committee and communicated to the Data Management Committee (DMC) who will ensure that confidentiality of data is ensured. The intervention coordinator and trial manager will

also report to the DMC any adverse events arising from the interventions, including situations in which additional interventions were required following disclosure of risk by a participant or during an assessment or intervention session. Independent Data and Safety Monitoring Committee (DSMC) will consist of experts not involved in the planning and conduct of this study, with no conflicts of interest or obligations to the investigator. A database of adverse events will be maintained by the DMC and annual reports will be sent to the Data and Safety Management Committee (DSMC). At the end of the study, data will be transferred on the University of Montreal's server (UNIX) (see Appendix O for bank protocol).

Exercises responses stored on the website will be secured. None of the answers given by participants will be analyzed as part of the study. These exercises are exclusively an educational tool from the intervention. Professionals and partners will not have access to this content.

The Parents and Babies program is a research project and is not part of the usual services provided. Personal outcomes from the intervention will not have any clinical impact that would require follow-up from the medical team. For this reason, participation will not be indicated in the participants' medical record. This intervention is validated in other populations (American pregnant women in the general population) and formats (in person 1:1 or group session, fully automated web-based course).

Risks to Participants

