Counseling interventions received a grade B recommendation from the USPSTF (2), reflecting the low level of risk and high probability of a moderate net benefit. None of the included studies, however, offered virtual counseling and there is very little evidence of the efficacy of virtual prevention interventions. As in all studies where participants report on their mental health, there is always the possibility that participants become more aware of their symptoms. We will minimize risk to participants by taking the following measures. First, at the end of each assessment, there will be a list of resources to manage mental health issues (Appendix M). The list will include contact information for: 1) in Quebec, Integrated University Health and Social Services Centres (CIUSS). These local community health centers offer prenatal classes, telephone call services, and links to psychosocial and mental health services; 2) family physician clinics; 3) obstetric clinics, and; 4) emergency phone numbers and help lines. Second, we will set up a telephone line to answer questions about the study and remind participants of available resources. Third, participants with a positive response on the EPDS self-harm ideation item or scoring above the clinical EPDS cut-off (≥ 13) during screening or follow-up will be notified by a pop-up at the end of the questionnaire. The pop-up will inform them they will receive a phone call from a nurse of our team and encourage them to speak to their doctor and contact resource links (Appendix N). The nurse will make the call within 24 hours to evaluate the suicidal risk and make sure the participant is taken in charge by appropriate health services.

Expected Results and Benefits

[figure not shown]
This project will 1) provide virtual support related to the program content to women with symptoms of depression (moderate severity) in a context where individual medical and psychosocial follow-ups are minimized due to the pandemic; 2) prevent the worsening of depression and anxiety, improve stress management, and potentially improve obstetric outcomes and prevent child development disorders associated with maternal disorders; 3) develop an online economic intervention for pregnant women in situations of social isolation or activity limitations due to various causes (e.g., pandemic, strict rest at home); 4) facilitate the coordination of virtual social support by maternal and child physical health specialists and

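### The Data Collection section can be read as letting a woman answer her outcome questionnaires with her partner, and no supplied section requires private completion

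*Combined protocol and SAP*

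**What the plan says.** Under Data Collection, the woman's questionnaires are done on REDCap or by telephone with a blinded research assistant, as she prefers, "and with the partner if the woman so chooses".

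Under Confidentiality and Privacy Protection, the protocol states: "Data will remain strictly confidential and will not be disclosed to members of our intervention team or the partner". The same section closes the website exercises to partners as well: "Professionals and partners will not have access to this content".

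Partners are also participants. The recruitment text says "Recruited pregnant women and partners will receive a notification with a link to answer the baseline questionnaire", and the secondary outcomes paragraph plans partner assessments at baseline, T1 and T2.

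Under Partners Recruitment, the coordinator asks about the partner during the woman's recruitment call, and "if he or she is at home at this moment, he or she will be invited to join the call". Under Pregnant Women Recruitment, the eligibility questions (EPDS, psychosis screen, substance abuse) are answered by telephone.

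The primary outcome is the proportion of women with EPDS ≥ 13 at 3 months. At the same visit the woman completes the DAS-7 on marital satisfaction and a co-parenting scale with items such as "partner appreciates how hard I work at being a good parent". Under Risks to Participants, a woman who endorses the EPDS self-harm item or scores 13 or more "will be notified by a pop-up at the end of the questionnaire", and a nurse then telephones within 24 hours.

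**The concern.** Taken at its plain grammar, the phrase about the partner describes how the woman's own questionnaire is completed, in parallel with the phrase about the research assistant. On that reading the plan allows the partner to hear or see her answers.

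Three things are then at stake:

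- **Primary outcome.** The EPDS is a self-report scale cut at 13. Reluctance to disclose low mood in front of the partner would lower the number of recorded events.
- **Couple outcomes.** The DAS-7 and the co-parenting scale concern the person who may be in the room. Answers given in front of that person are open to social desirability.
- **Safety disclosure.** The nurse's call depends on candid EPDS answers, and the on-screen notice could be seen by a partner sitting beside the woman.

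The protocol shields even the website exercises, which it does not analyse, from partners. It would be odd to give the outcome battery less protection.

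**Working it through.** This is mainly a question of text, so the passages are set side by side first. The arithmetic afterwards is illustrative only.

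**1. What the clause can mean.**

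- *Joint completion.* The grammar supports this. In addition, a partner's own participation depends on the partner's interest and consent (Partners Recruitment), not only on the woman's choice.
- *The partner's own forms.* Partners have their own baseline link and their own assessments, and under Partner participation it is the woman who decides whether to involve them. This reading is also tenable.

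**2. Whether another section settles it.** The supplied text contains no instruction to answer alone, no instrument exempted from joint completion, no record of who was present, and no sensitivity analysis for it. The confidentiality statement points towards privacy but does not say how forms are to be completed.

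**3. Which instruments are exposed, and when.** The EPDS is given at T0, T1 and T2. The DAS-7 and the co-parenting scale are given at 3 months only. Substance use is reported at baseline and 3 months.

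**4. The plan's own figure.** Inputs from the Sample size paragraph: 20% v 10%, 80% power, two-sided 5%, and two successive 10% losses.

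n per arm = [1.96·√(2·0.15·0.85) + 0.8416·√(0.20·0.80 + 0.10·0.90)]² / 0.10² = (0.990 + 0.421)² / 0.01 ≈ 199.

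199 / (0.9 × 0.9) ≈ 246 per arm, or 492 in total, against the stated 500. The sample size is reproduced and is not in question here.

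**5. Illustration of equal under-reporting in both arms.** Let u be the share of true EPDS ≥ 13 cases that are hidden. The documents give no value, so 0 to 30% is assumed. For example, u = 10% would arise if half of the women answered jointly and one in five true cases among them were concealed (0.5 × 0.2). With 250 × 0.9 = 225 analysed per arm, p₁ = 0.20(1 − u), p₂ = 0.10(1 − u) and p̄ their mean:

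power = Φ{[(p₁ − p₂) − 1.96·√(2p̄(1 − p̄)/225)] / √([p₁(1 − p₁) + p₂(1 − p₂)]/225)}

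| u | Observed rates | Difference (points) | Power |
|---|---|---|---|
| 0% | 20.0% v 10.0% | 10.0 | 84.6% |
| 5% | 19.0% v 9.5% | 9.5 | 82.4% |
| 10% | 18.0% v 9.0% | 9.0 | 80.0% |
| 20% | 16.0% v 8.0% | 8.0 | 74.4% |
| 30% | 14.0% v 7.0% | 7.0 | 67.9% |

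With equal concealment the observed difference shrinks towards zero, and power falls below the planned 80% only once more than about 10% of cases are hidden.

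**The case against.** The strongest reply is that the clause may only say, clumsily, that partners are assessed too. That stands as a possible reading and cannot be excluded. It does not remove the need for a change, because the sentence as written permits the other reading and nothing else rules it out. The questionnaires, tool descriptions and notice text are in appendices that were not supplied, so a privacy instruction may exist there.

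A reader might infer more than the documents support, in four ways:

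- **A flat contradiction with the confidentiality promise.** That promise concerns what the study discloses. A woman who chooses to answer beside her partner shares her own answers. This is a tension to reconcile, not a breach.
- **A spurious treatment effect.** The sentence about adapting calls to the woman and/or her partner concerns the frequency of intervention calls, not who is present at assessments. Partners are raised at recruitment for everyone, before allocation, and the control group gets an automated version of the same programme. Nothing shows that presence would differ by arm.
- **No nurse call for any woman who hides the self-harm item.** A score of 13 or more triggers the call as well, so a woman is missed only if both triggers are missed. The described content of the notice does not say which trigger was met.
- **Bias from the recruitment call.** Screening precedes randomisation, so it cannot bias the comparison of arms. The text does not say when the partner joins relative to the eligibility questions. The remaining concern is privacy and candour at screening.

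**Conclusion.** The point holds as a permissive and ambiguous rule that should be tightened. Followed literally, it allows joint completion of a battery that contains the self-reported primary outcome, a safety trigger and two scales about the couple. Under-reporting and socially desirable answers are then a risk, not an established fact.

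The size cannot be derived from the documents. The power figures rest on an assumed share of hidden cases, equal in both arms, with 225 women per arm. No figure is offered for the DAS-7 or the co-parenting scale, because any would be invented. The safety concern needs no assumed rate, but it is limited to women whose answers avoid both triggers.

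**What to change.** Replace the clause in Data Collection with a statement that each woman and each partner completes her or his own questionnaire separately and in private. This would be done through individual REDCap links, or by telephone after the assistant has confirmed that the respondent can speak privately. That also brings the section into line with the confidentiality statement.

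In the recruitment script, state that the partner joins only for the explanation of the study and is not on the call while the EPDS, psychosis and substance-use questions are asked.

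Add one item at T0, T1 and T2 asking whether anyone was present while the form was answered, and report it by arm. No arm difference is presumed. The item makes the question checkable, and presence cannot be reconstructed afterwards.

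The cost is a reworded sentence, a line in the call script and one questionnaire item. Partners already receive a baseline questionnaire link, so little new infrastructure is needed. The small downside is that an occasional call must be rescheduled.

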Sample size. A meta-analysis of 58 studies indicates that the overall prevalence of postpartum depression is 17% (95% CI: 0.15–0.20) (53). This estimate falls within previously published estimates of 13%–19.2% (54, 55) and is similar to Hahn-Holbrook's 2018 finding of 17.7%. In-person interventions using the *Mother & Babies* course reported moderate effect sizes (OR = 0.28 (0.08-0.94) (22) and OR = 0.45 (0.19-1.10) (24)). Fully web-based without nurse-based telephone support reported small to moderate effect sizes (40). Given that the proposed intervention is offered virtually with nurse-based telephone support, we calculated a sample size that allows us to detect a moderate decrease in rates of clinical depression. We anticipate that 20% of pregnant women in the control group will have an EPDS score ≥ 13 at postpartum. A total of 500 pregnant women (250 per arm) is needed to detect an absolute reduction of 10% (i.e., 20% of women with EPDS ≥ 13 in the control arm versus 10% in the intervention arm) with 80% of power and a 2-tailed alpha of 5%. The sample size includes an attrition rate of 10% for 3 months' postpartum and another 10% between 3 and 6 months' postpartum. Based on our experience with pregnant women and the intervention (see Section about Pilot Study), the 10% attrition estimate is conservative. As most of the secondary

outcomes are continuous, the sample size provides enough power to detect small to moderate effect sizes using a 2-tailed alpha of 1% to account for multiple tests.

Compliance. We conducted a feasibility pilot study including 17 pregnant women. All began to read the online material and 2 refused further participation after 2 telephone calls, a dropout rate of 11.7%. We therefore expect that 80-90% of the intervention group will read at least some of the intervention material. Intervention compliance will be defined as completion of a minimum of 6/8 online modules and 6/10 telephone follow-ups. Compliance will be monitored automatically online and by nurses during telephone calls. Weekly text reminders will be sent out to maximize compliance (see details in Appendix H).

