
support or attachment, social integration, reassurance of worth, tangible help, orientation, and opportunity for nurturance (96, 97).

Parent and child assessments. Maternal depression has repeatedly been associated with poorer quality mother-infant relationships, attachment, and child-emotional development. **Parenting** will be assessed at 6 months postpartum with the Parent's Cognition and Conduct Toward the Infant Scale (ÉCOPAN) (98). **Child social, emotional and cognitive development.** The Ages and Stages Questionnaire 3rd edition (ASQ-3) is a widely used parent-reported scale covering physical, social, emotional, and cognitive child development at ages one month to 5 ½ years. Its parent-centric approach and inherent ease of use have made it the most widely used developmental screener in the world (99). **Child difficult temper** will be evaluated at 6 months postpartum with the Infant Characteristics Questionnaire (ICQ) (100, 101).

Other variables (effect modifiers). **Compliance to the intervention.** Participant and partner use will be calculated automatically using web-based statistics and the number of modules completed will be self-reported. The number of calls with the nurses will also be recorded. **Intervention Team Activity Log.** All intervention activities (telephone discussions, voice messages, missed sessions) will be documented. **Personality disorders symptoms.** These may be important modifiers of the intervention and thereby impact compliance. We will use the 25-item Personality Inventory for DSM-5 Brief Form (PID-5 BF) (102). Groups will be created using a 30% cut-off score for each subscale. **Gender roles.** Using data at T₂ we will create a gender role score for participants and partners by identifying gender-related variables such as employment status, income; gender roles assessed using the Bem Sex Role Inventory (BSRI) (103, 104). Sex of the child will also be tested as a potential effect modifier. **The sociodemographic and medical history.** Information will be collected about the household, employment status, revenue, education level, ethnicity, reproductive history, COVID-19 infection history and weight.

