Economic evaluation. Service utilization will be measured using a slightly modified version of the **Health Service Utilization and Cost of Care Questionnaire** (105) to assess childcare expenses and travel costs incurred by patients to obtain care. Costs of administering the intervention include a) recruiting and training of nurses, b) nurses' time to provide the intervention, and c) supervision of nurses.

Planned Analyses

Data will be analyzed using SAS software using an intent-to-treat approach. A two-sided significance level of 0.05 will be used for the primary outcome; a significance level of 0.01 (two-sided) will be used for secondary and other outcomes to account for multiple outcomes. Demographic and other baseline variables will be compared between study groups using descriptive statistics (mean, standard deviation, proportions).

For the primary outcome, a two-sample sided test of proportion (chi-square test) will be used to compare the difference in the proportion of women with EPDS in the clinical range (> 13) at 3 months' postpartum. The same approach will be used for the 6-month assessment (secondary outcome). These analyses will be supplemented by an analysis using EPDS scores, where the baseline EPDS score will be used as covariate in an ANCOVA model including the 3- and 6-month EPDS scores. With this model, we will obtain 95% confidence intervals of EPDS score differences between intervention arms at 3 and 6 months' postpartum. Sensitivity analyses will be performed to investigate the potential bias introduced

by attrition. A method based on inverse-probability-of-attrition weights (IPAWs) will be used (101, 102).

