For secondary outcomes, the statistical method for comparing intervention arms will depend on the distribution of the outcome variable. For binary variables, chi-square tests will be used. The corresponding 95% CI for the difference in proportions will also be provided. In the unlikely event that randomized intervention arms are unbalanced for baseline variables known to be associated with primary and secondary outcomes, logistic regression will be used where unbalanced variables will be included. For continuous variables, we will use ANCOVA models as described above. Again, unbalanced variables will be added if needed. If the intervention is found to be effective, exploratory analyses will be conducted to explore the potential effect of moderator variables using causal inference models including gender and intervention compliance (103, 104). No formal interim efficacy analysis is planned. Ethical practices and conduct of the trial as well as all safety concerns will be reported to an independent Data and Safety Monitoring Committee.

Planned subgroup analyses. The ANCOVA models presented above will be expanded to include the socioeconomic status of the participant, ethnicity, personality disorder symptoms subgroup variable as well as interaction with the intervention.

Pilot Study

We conducted a feasibility study to assess acceptability and compliance to the intervention (n = 17). Pilot data indicate that women used a mix of electronic devices to access the intervention. All used an iPad at some time, 40% also used their smartphone and 20% also used a computer. Telephone follow-up by a nurse was rated as “essential” (40%), “very useful” (40%), or “useful” (20%). Online sessions were rated as “very useful” (60%) or “useful” (40%). Strategies proposed in the intervention (cognitive restructuring, relaxation, behavioral modification, social support) were used “regularly” (30%), “often” (50%), “occasionally” (10%), or “never” (10%). The material was rated as “very easy to understand” (90%) or “easy” (10%). Each strategy was used at least occasionally by 86% of women. Qualitative data indicated high levels of appreciation (Appendix A).

Ethical considerations

Voluntary informed consent

The recruiting process will allow women to give a voluntary informed consent (Appendix E). The consent form will be signed on the online platform provided by the URCA.

Confidentiality and Privacy Protection

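### Personality scores are grouped at an undefined 30% cut-off before the moderator test, and no analysis of the continuous scores is planned

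*Combined protocol and SAP*

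**What the plan says.** In the combined protocol and SAP, *Other variables (effect modifiers)* names the 25-item PID-5 Brief Form as the measure of personality disorder symptoms and gives one rule for using it: "Groups will be created using a 30% cut-off score for each subscale".

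*Planned subgroup analyses* then expands the ANCOVA models to include, along with socioeconomic status and ethnicity, a "personality disorder symptoms subgroup variable as well as interaction with the intervention".

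Three other places bear on the point:

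- *Research Questions* lists personality disorder traits among the moderators in the tertiary question.
- *Planned Analyses* says "If the intervention is found to be effective, exploratory analyses will be conducted to explore the potential effect of moderator variables".
- *Planned Analyses* also sets the level outside the primary outcome: "a significance level of 0.01 (two-sided) will be used for secondary and other outcomes to account for multiple outcomes".

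No model using the ungrouped subscale scores is described, and no effect size or power is given for any interaction.

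**The concern.** A questionnaire subscale gives a graded score. Grouping it treats all women on one side of the cut as alike and assumes that the treatment effect changes only at the cut. If the effect changes gradually with the score, variation within groups is lost and a real moderator becomes harder to detect.

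The rule is also incomplete as written. A 30% cut-off could mean the top 30% of the sample, the bottom 30%, both tails, or 30% of the maximum score. The grouping is made for each subscale, while the model is described with a single subgroup variable, and nothing says how the subscales combine. The moderator result would therefore depend on a choice that the text leaves open.

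The plan handles its main outcome differently: the dichotomised EPDS comparison is supplemented by an ANCOVA on the EPDS scores. Personality symptoms have no such supplement.

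**Working it through.** **1. The plan's own sample size.** *Sample size* assumes "20% of women with EPDS ≥ 13 in the control arm versus 10% in the intervention arm", 80% power and two-sided alpha 5%. With a mean rate of 0.15:

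n per arm = [1.960 × √(2 × 0.15 × 0.85) + 0.842 × √(0.20 × 0.80 + 0.10 × 0.90)]² / 0.10² = 199.

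Two successive 10% losses leave 0.9 × 0.9 = 0.81, and 199/0.81 gives 246 per arm, or 492. Dividing by 0.80 instead gives 249 per arm, or 498. The stated 500 reproduces. It is sized on the main effect for the primary outcome only.

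**2. Women available.** 500 × 0.9 = 450 at 3 months; 450 × 0.9 = 405 at 6 months.

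**3. Information kept after grouping.** Assumptions not in the documents: a normal score and a moderating effect linear in the score. For two groups with share p above the cut c, the relative efficiency is φ(c)²/[p(1 − p)].

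| Reading of the rule | Efficiency | Loss |
|---|---|---|
| Two groups, 30/70 (either tail) | 0.3477²/0.21 = 0.576 | 42% |
| Three groups, 30/40/30, scored as a trend | 2 × 0.3 × (0.3477/0.3)² = 0.806 | 19% |
| Score-value cut, 50% above | 0.3989²/0.25 = 0.637 | 36% |
| Score-value cut, 20% above | 0.2800²/0.16 = 0.490 | 51% |
| Score-value cut, 10% above | 0.1755²/0.09 = 0.342 | 66% |

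Under the 30/70 reading, 450 women carry the information of 450 × 0.576 = 259, and the standard error is 1/√0.576 = 1.32 times larger.

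Normality matters. For right-skewed scores (gamma with shape 2, and exponential, both simulated), a top-30% cut loses about 36% to 38% and a bottom-30% cut about 62% to 70%.

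**4. Interaction power.** Take residual SD 1, a standardised moderator, and b as the difference between arms in slope per moderator SD. The noncentrality is b × √(efficiency × N/4). The values of b are assumptions. For N = 450 and b = 0.3, it is 0.3 × √112.5 = 3.18 for the continuous score and 3.18 × √0.576 = 2.41 for the split, against a critical value of 2.576 at alpha 0.01.

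| b | Continuous, alpha 0.01 | 30/70 split, alpha 0.01 | Continuous, alpha 0.05 | 30/70 split, alpha 0.05 |
|---|---|---|---|---|
| 0.2 | 32.5% | 16.7% | 56.4% | 36.3% |
| 0.3 | 72.8% | 43.6% | 88.9% | 67.5% |
| 0.4 | 95.2% | 74.0% | 98.9% | 89.6% |

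The 0.05 columns are shown because the plan sets 0.01 for secondary and other outcomes without naming interaction tests. With 405 women and alpha 0.01, the pairs are 28.7% against 14.7%, 67.1% against 38.8%, and 92.6% against 68.4%.

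**The case against.** **The size is not fixed by the documents.** A reader might infer that the plan throws away 42% of the information and leaves 450 women worth about 260. That needs exactly two groups, a cut at the 30th or 70th percentile, a normal score and a linear effect. The text states none of these. This objection stands: 42% is one case in a range.

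**Low power is not shown in general.** A reader might also infer that the interaction test is underpowered however it is done. The documents give no interaction effect size. At alpha 0.01 with 450 women, the continuous test has 32.5% power at b = 0.2 but 95.2% at b = 0.4. Low power is a fair description of modest moderation only.

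**The analysis is minor.** Moderators are a tertiary question, and *Planned Analyses* makes moderator work exploratory and conditional on efficacy. The separate subgroup paragraph does not repeat that condition, so whether it covers this model is unclear. Either way, the primary test and the sample size are untouched.

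**A group contrast is a legitimate question.** If the effect really changes at a threshold, a linear term is misspecified and its advantage can shrink or reverse. This stands as a limitation, but the protocol text gives no reason to expect a threshold at 30%, and displaying the groups alongside covers it.

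**The cut-off may be justified elsewhere.** The assessment tools are described in Appendix L and the instrument is cited to a validation paper; neither is available here. So the cut cannot be called arbitrary, only undefined in the protocol text.

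**Conclusion.** The point holds as a minor one. The plan groups each PID-5 BF subscale by a rule that the protocol text does not define, tests the grouped variable against arm, and describes no analysis of the scores themselves. With roughly linear moderation, every grouping examined loses information: from about 19% (30/40/30) to 66% (score-value cut with 10% above) for a normal score, and up to about 70% for a bottom-30% cut on a skewed one. With 450 women, alpha 0.01 and a 30/70 split, the cost is between about 16 and 29 percentage points of power over the slope differences tried. These sizes rest on linearity, the assumed score distribution and the assumed slopes. The missing definition rests on no assumption. Nothing here bears on the primary conclusion.

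**What to change.** In *Planned subgroup analyses*, make arm by continuous, standardised PID-5 BF subscale score the main moderator test in the planned ANCOVA models, and report the estimated treatment effect, with its confidence interval, at stated low and high scores.

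Keep the groups for supplementary display only. In *Other variables (effect modifiers)*, define the 30% rule before outcome data are seen: percentile or score value, which direction, how many groups, and how the subscales are handled, singly or combined.

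The cost is SAP wording, with no new data or participants. The one small downside is that a linear term can miss a threshold effect, which the displayed groups would help to show.
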